9. STUDY ASSESSMENTS AND PROCEDURES

The Schedule of Assessments and Procedures is located in Table 2.1. Unless otherwise noted, the assessments and procedures should be conducted in person by the Investigator or designee.

Any protocol-required evaluations (eg, laboratory tests and) already done locally on the corresponding study day, including baseline, as part of the subject's regular medical care can be recorded on the eCRFs and do not have to be repeated for purposes of this study.

9.1.Baseline

Baseline procedures must be completed within 24 hours before the start of the first dose of IV study drug. Potential subjects who do not meet entrance criteria may, as appropriate, repeat baseline evaluations at a later time for possible enrollment into the study.

- Obtain informed consent in writing from parent(s) or legally acceptable representative(s) and assent from subject (as applicable) before initiating any study assessment or procedure.
- Collect demographic information including age, gender, race and ethnicity.
- Clinical Assessments (assessments will be performed for research unless they are already being performed per standard of care; exceptions are indicated):
 - Obtain a complete medical and surgical history, including history of surgical procedures for complications of hematogenous SA osteomyelitis (eg, drainage of the bone) and all active conditions and all conditions diagnosed within the previous 5 years (from the following categories: allergic; cardiovascular; dermatological; gastrointestinal; genital and reproductive; head, eyes, ears, nose, and throat; hematology; hepatic; immunological; metabolic and endocrine; musculoskeletal;

neurologic; psychiatric; renal; and respiratory).

- o Record prior medications (Section 8.3) taken or received within 14 days before the first dose of study drug. For children who are being breast fed, record all medications taken by the lactating mother during the 3 days before the first dose of IV study drug. In addition, record history of pneumococcal vaccinations.
- o Record standard of care radiology results.

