9.3. Study Days 2-14

The total duration of IV ceftaroline is dependent on the subject's response to therapy but 5-14 days is anticipated in most subjects. If the subject is able to switch to oral drug before Day 15, the procedures outlined for Day 15 (EOIV) should be performed. The rest of the visit schedule will be followed as described in Table 2.1.

- Study Drug Administration:

IV ceftaroline fosamil **15 mg/kg** (or 600 mg if > 40 kg) infused over 120 (\pm 10) minutes q8h (\pm 1 hour) for children **2 years of age – 17 years** of age (inclusive).

IV ceftaroline fosamil **10 mg/kg** infused over 120 (\pm 10) minutes q 8h (\pm 1 hour) for children from **1 year of age to < 2 years** (inclusive) until the subject transitions to oral therapy.

- Clinical Assessments – any time during study day (assessments will be performed for research unless they are already being performed per standard of care; exceptions are indicated):
 - Record concomitant medications (Section 8.3). For subjects who are being breast fed, record all medications taken by the lactating mother.
 - Record resting vital signs (pulse, blood pressure, and respiratory rate), and highest postdose temperature measured.
 - Record adjunctive therapeutic procedures (eg, surgeries).
 - Record standard of care radiology results.
 - Evaluate and record physical findings of hematogenous SA osteomyelitis (eg, warmth, tenderness, swelling, erythema, and movement of the infected extremity). Most of the subjects are expected to have surgical incision and drainage procedures and thus assessing the extremity for swelling, erythema, warmth and tenderness may not be possible because of drains in place and large surgical dressings that cannot be removed. The degree of the subject's ability to ambulate will be assessed if the osteomyelitis is in the lower extremity- ie. walks unaided, able to bear weight, can walk aid using a walker, etc. The use of upper and lower extremities will be assessed in terms of movement and range of motion.
 - Identify, assess, and record any new or ongoing AEs or SAEs
- Laboratory Assessments – any time during the study period if clinically indicated (assessments will be performed for research unless they are already being performed per standard of care; exceptions are indicated):
 - Collect CRP and ESR lab results, if clinically indicated.
 - Collect CBC with differential, BUN, and Creatinine, lab results, if clinically indicated.

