9.4. Study Day 15 (End of IV Treatment-EOIV)

The total duration of IV ceftaroline is dependent on the subject's response to therapy but 5-14 days is anticipated in most subjects. If the subject is able to switch to oral drug before Day 15, these procedures may be performed before Day 15. Conduct EOIV assessments within 24 hours after administration of the last dose of IV study drug (subjects will likely remain in the hospital for less than 24 hours once they are transitioned to oral therapy as per standard of care) or at time of premature discontinuation of study drug or early withdrawal from study (if on IV study drug). Conduct the EOIV assessments in place of the regular study visit assessments that would have been performed the day of that visit. A subject may be eligible to switch to PO drug on or after Study Day 3 (Section 9.2). EOIV assessments must occur before starting PO drug. The rest of the visit schedule should be followed as described in Table 2.1.

If applicable, as IV study drug may or may not be given on the same calendar day as EOIV assessments, administer IV study drug IV ceftaroline fosamil **15 mg/kg** (or 600 mg if > 40 kg) infused over 120 (\pm 10) minutes q8h (\pm 1 hour) for children **2 years of age – 17 years** of age (inclusive).

IV ceftaroline fosamil **10 mg/kg** infused over 120 (\pm 10) minutes q 8h (\pm 1 hour) for children from **1 year of age to < 2 years** (inclusive) until the subject transitions to oral therapy.

- Clinical Assessments - any time during study day, but before starting PO study drug, if applicable (assessments will be performed for research unless they are already being performed per standard of care; exceptions are indicated):
 - Record concomitant medications (Section 8.3). For subjects who are being breast fed, record all medications taken by the lactating mother.
 - Record vital signs: resting pulse, blood pressure, and respiratory rate; and highest daily temperature measured.
 - Record adjunctive therapeutic procedures (eg, surgeries).
 - Record standard of care radiology results.
 - Evaluate and record physical findings of hematogenous SA osteomyelitis (eg, warmth, tenderness, swelling, erythema, and movement of the infected extremity). Most of the subjects are expected

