to have surgical incision and drainage procedures and thus assessing the extremity for swelling, erythema, warmth and tenderness may not be possible because of drains in place and large surgical dressings that cannot be removed. The degree of the subject's ability to ambulate will be assessed if the osteomyelitis is in the lower extremity- ie. Walks unaided, able to bear weight, can walk aid using a walker, etc. The use of upper and lower extremities will be assessed in terms of movement and range of motion.

- o Assess clinical outcome (site of infection has complete resolution of pain, swelling and warmth and the patient is able to use the affected extremity normally and is back to normal activities).
- o Identify, assess, and record any new or ongoing AEs or SAEs. Subjects will likely remain in the hospital for less than 24 hours once they are transitioned to oral therapy as per standard of care.
- Laboratory Assessments- any time during study day, but before starting PO drug, if applicable. If these assessments are performed within 48 hours of latest results, do not repeat these assessments (assessments will be performed for research unless they are already being performed per standard of care; exceptions are indicated):
 - o Collect CRP and ESR lab results.
 - o Collect CBC with differential, BUN, and Creatinine.
 - o Obtain blood sample for AST, ALT, Alkaline Phosphatase, Bilirubin and Direct Coombs.
 - o If clinically indicated, estimate CrCl using the updated Schwartz "bedside" formula (Schwartz et al, 2009).
 - o Collect results of blood cultures for *S. aureus* only if conducted per standard of care.
 - o Collect purulent material from bone only if a procedure is performed for standard of care when possible.

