9.8. Safety Lab Tests

9.8.1. Study Required Lab Tests

Alkaline Phosphatase, Bilirubin, AST, ALT and Direct Coombs (DATscreen) will be obtained within 24 hours prior to enrollment; and at the completion of ceftaroline treatment (EOIV visit).

Isolate susceptibilities: The ceftaroline MIC of *S. aureus* isolates or other isolates such as Group A streptococcus, *Streptococcus pneumoniae* or *Kingella kingae* that are obtained from the patients with acute hematogenous osteomyelitis will be determined using Clinical and Laboratory Standards Institute (CLSI) methods. These will be performed in the CAP certified Infectious Disease Research Laboratory. CLSI interpretive breakpoints will be used to determine if the isolate is susceptible, intermediate or resistant to ceftaroline. The samples will be obtained from pathology (from already collected samples) to conduct the Isolate susceptibility studies.

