12.4. Safety Analysis

Adverse event and serious adverse event monitoring, vital signs and laboratory tests (CBC, BUN, Creatinine, Bilirubin, Alkaline Phosphatase, AST and ALT will be obtained within 24 hours prior to enrollment and weekly during ceftaroline treatment and at the completion of ceftaroline treatment). The Alkaline Phosphatase, Bilirubin, AST/ALT results may not be available prior to enrollment of the patient.

We do not anticipate that the AST/ALT concentrations will be > 3 UNL but if they were to be this elevated, the patient subject will be dropped from the study immediately.

Safety parameters include AEs, SAEs, deaths, clinical laboratory parameters (eg, hematology parameters, chemistry parameters), and vital signs. For each safety parameter, the last assessment made before the first dose of IV study drug will be used as the baseline for all analyses.

The incidences of TEAEs, SAEs, deaths, and discontinuations due to AEs will be summarized by system organ class and preferred term according to the Medical Dictionary for Regulatory Activities by relationship to the study drug, and by severity.

Descriptive statistics of observed results and the change from baseline will be presented for clinical laboratory results, and vital signs. The incidence of PCS laboratory results will be summarized.

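### A pre-dose sample can meet Section 9.4's 48-hour no-repeat rule, so a child stopped within 24 to 48 hours of the first dose may have no post-exposure safety labs

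*Combined protocol and SAP*

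**What the plan says.** - **EOIV labs (Section 9.4).** The list is CRP, ESR, CBC with differential, BUN, creatinine, AST, ALT, alkaline phosphatase, bilirubin and Direct Coombs. The instruction in front of it reads: "If these assessments are performed within 48 hours of latest results, do not repeat these assessments".
- **EOIV timing (Section 9.4).** "Conduct EOIV assessments within 24 hours after administration of the last dose of IV study drug"; for children who stop early, "or at time of premature discontinuation of study drug or early withdrawal from study (if on IV study drug". On that day the EOIV visit supersedes the ordinary one: "Conduct the EOIV assessments in place of the regular study visit assessments that would have been performed the day of that visit". Section 7.8.1 sends safety discontinuations to this visit.
- **Baseline (Section 9.1).** "Baseline procedures must be completed within 24 hours before the start of the first dose of IV study drug". The baseline list includes the CBC, renal and liver tests and the Direct Coombs.
- **Between baseline and EOIV (Section 9.3).** "Collect CBC with differential, BUN, and Creatinine, lab results, if clinically indicated". The liver panel carries the same condition, and so does footnote 7 of Table 1.1 for CBC and chemistries. Table 1.1 has no CBC, chemistry or Coombs on Day 1, and no Coombs on Days 2-14.
- **At the end of ceftaroline.** Section 9.8.1 says that the liver tests and Coombs "will be obtained within 24 hours prior to enrollment; and at the completion of ceftaroline treatment (EOIV visit". Section 12.4 asks for CBC, BUN, creatinine and liver tests every week on drug and again when ceftaroline ends. Neither section mentions 48 hours.
- **Analysis.** Section 12.4 takes as reference "the last assessment made before the first dose of IV study drug will be used as the baseline for all analyses" and reports observed values and change from it. Section 12.1 puts every child with one dose in the safety analysis. Section 6.1 lists laboratory parameters under the primary outcome.

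**The concern.** The no-repeat rule looks only at the age of the most recent result, not at whether the child had been exposed to ceftaroline when the blood was drawn. In the first two days the most recent result can be the baseline. A child who stops then reaches EOIV with a pre-dose sample less than 48 hours old, and the site is told not to draw another.

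The primary objective is safety at the end of IV therapy, and laboratory values are part of it. An early-stopped child remains in the safety set and is not replaced, because Section 7.9 replaces only children who received no drug. Table 1.1 schedules no CBC, chemistry or Coombs after EOIV, so no planned draw makes good the gap. The most plausible cases are clinical reactions such as rash or diarrhea, where the remaining labs would show whether anything else was affected.

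**Working it through.** **1. The plan's own figure.** The only design figure stated is N = 18 (Section 6.2, A'Hern single-stage, 0.50 versus 0.80, alpha 0.05, power 80%). An exact binomial search with one-sided alpha gives n = 18 with at least 13 successes: attained alpha 0.0481, power 0.867. So 18 reproduces. It is not in dispute and serves here only as the denominator.

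**2. When a pre-dose sample meets the rule.** Let b be the hours from baseline draw to first dose (0 to 24, Section 9.1) and t the hours from first dose to the EOIV assessment. With the clock run from the draw, the sample is b + t hours old at EOIV, so the condition is b + t ≤ 48, or t ≤ 48 − b. Doses are q8h, starting at 0, 8, 16, … hours.

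| b (h) | Latest t = 48 − b (h) | Doses started before t |
|---|---|---|
| 0 | 48 | 6 |
| 6 | 42 | 6 |
| 12 | 36 | 5 |
| 18 | 30 | 4 |
| 24 | 24 | 3 |

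Every EOIV within 24 hours of the first dose is exposed whatever b is. Between 24 and 48 hours it depends on b. Beyond 48 hours none is.

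**3. Who falls outside.** Section 8.4 requires at least 48 hours of IV drug before an oral switch. A baseline drawn before the first dose is then more than 48 hours old, so no planned switch is affected.

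**4. Which stops fall inside.** Section 7.7.1 has seven toxicity criteria. Five are laboratory-defined (creatinine clearance, neutrophils, hemolytic anemia, platelets, AST/ALT) and two are clinical (diarrhea, rash). A stop on an on-treatment result has a post-dose value for that analyte. The gap therefore concerns clinical stops and panels that were not redrawn. One laboratory case remains: Section 1 allows dosing before the baseline liver results are back, and a child dropped on a late-reported baseline AST/ALT has only that pre-dose sample.

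**5. Ambiguous clock.** Section 9.4 does not say whether the 48 hours run from draw or from report. Where baseline liver results come back after dosing, a report-time clock would extend the window past the table above. The documents do not allow the extension to be quantified.

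**6. What one such child does to the summary.** Share of the safety set: 1/18 = 5.6%.
- If baseline is entered as the EOIV value, the change is 0. With mean change m in the other 17, the reported mean is (17m + 0)/18 = 0.944m.
- If the value is missing, the denominator is 17. For an abnormality seen in no child, the two-sided 95% exact upper bound is 1 − 0.025^(1/17) = 19.5%, against 1 − 0.025^(1/18) = 18.5% if the child is wrongly counted as tested and normal.

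**7. After the fix.** If only samples drawn after the first dose count, the exposed window is 0 hours. N stays at 18.

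**The case against.** The strongest reply is that the window is narrow and perhaps empty. Sections 9.3 and 9.4 anticipate 5 to 14 days of IV drug in most children, Section 1 treats 48 hours of drug as the minimum for assessing safety, and no rate of stops before 48 hours is given. This stands as a limit on frequency. It does not remove the child from the analysis, since Section 12.1 needs only one dose.

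Second, 9.8.1 and 12.4 can be read as the general requirement and 9.4 as the operating rule for the same visit. That is a fair reading, but it leaves the operating rule permitting what the general requirement does not, with no cross-reference. It is a conflict to reconcile.

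Third, other provisions may supply data: clinically indicated labs (9.3), recording of standard-of-care CBC, BUN and creatinine (9.8.2), follow-up of unresolved adverse events (10.5), and a hemolysis work-up if hemoglobin falls markedly (10.9). These reduce the loss, but all depend on clinical judgment or local practice, and none guarantees a post-dose sample.

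Fourth, sparing children a repeat draw within 48 hours is a sensible design choice. It stands in full for samples drawn on treatment.

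**Conclusion.** The defect is real, small in extent and cheap to remove. As written, a treated child whose EOIV falls within 24 to 48 hours of the first dose can satisfy the EOIV lab requirement with a pre-dose sample, Direct Coombs included, and so have no post-exposure value for panels not redrawn. This assumes that no interim draw was clinically indicated and that the clock runs from the draw. The number affected cannot be computed from the documents; each such child is 5.6% of the safety set.

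Three stronger readings are tempting and are not supported:
- A reader might infer that early stops show zero laboratory change by construction. Section 9.4 says not to repeat the tests; it does not say to enter baseline as the EOIV value. There is no carry-forward rule, and Section 12.8 only has missing data noted. The result is zero change or a missing value, depending on practice.
- A reader might infer that toxicity stops in general are hidden. Stops on an on-treatment laboratory value are not, for that analyte.
- A reader might infer a bias toward no effect across the trial, because 48 hours is 6 q8h doses: 6/15 = 40% of a 5-day course or 6/42 = 14% of a 14-day course. These are upper bounds that need an interim draw exactly 48 hours old and EOIV at the last dose. Such a sample is still on-treatment data, taken after 9 of 15 doses in the 5-day case. The same limit applies to Coombs: in a 5- to 14-day course the baseline Coombs is well over 48 hours old and 9.4 requires a new one.

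**What to change.** - **Section 9.4:** state that only samples drawn after the first dose count toward the 48-hour exemption, and that the 48 hours run from the time of draw.
- **Sections 9.4, 9.8.1, 12.4 and Table 1.1:** reconcile them so that the requirement for labs at completion of ceftaroline and its exemption read the same everywhere.
- **Section 12.4:** state that a pre-dose sample is never used as a post-baseline value; where no post-dose sample exists, list the value as missing.

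The defect does not require a tighter limit on the age of on-treatment samples, or a bar on the exemption for every early stop. The latter would force a redraw even where a post-dose result a few hours old had prompted the stop.

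The cost is a few sentences and at most one small blood draw, already on the EOIV schedule, in a few early-stopping children. Sample size and analysis are otherwise unchanged.

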Subject Participation: The duration of subject participation from signing the informed consent form will be up to 14 months (includes screening period, study drug administration, oral drug administration and a follow-up visit 12 months after the last dose of study drug). Baseline assessments for study eligibility will occur within 24 hours before the first dose of study drug except for Alkaline Phosphatase, Bilirubin, AST/ALT which will be obtained prior to administration of ceftaroline but the results may not be available. A minimum of 2 days (48 hours) of study drug administration is required to assess safety.

Test Product, Dosage, and Mode of Administration: IV ceftaroline fosamil **15 mg/kg** (or 600 mg if > 40 kg) infused over 120 (\pm 10) minutes q8h (\pm 1 hour) for children **2 years** of age – **17 years** of age (inclusive). IV ceftaroline fosamil **10 mg/kg** infused over 120 (\pm 10) minutes q8h (\pm 1 hour) for children from **1 year of age to < 2 years** (inclusive).

Isolate susceptibilities: The ceftaroline MIC of *S. aureus* isolates or other isolates such as Group A streptococcus, *Streptococcus pneumoniae* or *Kingella kingae* that are obtained from the patients with acute hematogenous osteomyelitis will be determined using Clinical and Laboratory Standards Institute (CLSI) methods. These will be performed in the CAP certified Infectious Disease Research Laboratory. CLSI interpretive breakpoints will be used to determine if the isolate is susceptible, intermediate or resistant to ceftaroline.

Oral Switch: A switch to one of the following open-label PO drugs is expected/allowed on or after EOIV assessments are completed and if criteria in Section 9.2 are met:

- PO clindamycin 13 mg/kg/dose q8h in subjects with proven MRSA infection due to clindamycin susceptible MRSA or if no pathogen is isolated.

OR

- PO cephalexin 25 to 33 mg/kg/dose q 8 hours in subjects with proven MSSA infection.

OR

- PO linezolid 600 mg q12h (Children > 12 years old) or 10 mg/kg q8h (children < 12 years old) in subjects with clindamycin-resistant MRSA pathogens or for patients with MRSA isolates who are unable to tolerate clindamycin.

Inclusion Criteria: Subjects are required to meet the following inclusion criteria:

1. Informed consent in writing from parent(s) or other legally acceptable representative(s) and assent from subject (if appropriate according to local requirements).
2. Male or female 1 to 17 years of age.

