3. Suspected hematogenous SA osteomyelitis in a large bone (upper or lower extremities, pelvis) based on clinical findings and radiology results.
4. One to three sites of osteomyelitis with expectation that transition to oral antibiotics will be likely prior to discharge to complete IV therapy (The second or third site might be contiguous like a proximal tibia and distal femur but could also be at sites unrelated such as a distal femur and pelvic bone).
5. Female subjects who have reached menarche must have a negative urine pregnancy test.
6. Female subjects who have reached menarche and are sexually active must be willing to practice sexual abstinence or dual methods of birth control (eg, condom or diaphragm with spermicidal foam or gel) during treatment and for at least 28 days after the last dose of any study drug.
7. Sufficient IV access to receive medication.

Exclusion Criteria: Subjects must **NOT** meet any of the following exclusion criteria. Septic arthritis contiguous to the site of osteomyelitis is not an exclusion criterion.

1. Received more than 24 hours of IV antibiotics prior to enrollment.
2. More than three bones infected.
3. Disseminated infection or is admitted to the pediatric intensive care unit.
4. Underlying condition (excludes mild eczema or reactive airways disease).
5. Suspected or proven venous thrombosis or concern for endocarditis.
6. Requirement for other reasons for another antibiotic potentially active against organisms commonly causing osteomyelitis in children.
7. Creatinine clearance < 50 mL/min/1.73m² (calculated by the Schwartz formula).
8. AST or ALT > 3 times the upper limit of normal.
9. Neutropenia (<500 neutrophils/mm³).
10. Thrombocytopenia (<50,000 platelets/mm³).
11. Females who are currently pregnant or breast feeding.
12. Hypersensitivity reaction to any Beta-lactam antibiotic.
13. Has had an allergic reaction to ceftaroline in the past.

Safety: Adverse event and serious adverse event monitoring, vital signs and laboratory tests (CBC, BUN, Creatinine, Alkaline Phosphatase, Bilirubin, AST and ALT will be obtained within 24 hours prior to enrollment and weekly during ceftaroline treatment and at the completion of ceftaroline treatment). The Alkaline Phosphatase, Bilirubin, AST/ALT results may not be available prior to enrollment of the patient. We do not anticipate that the AST/ALT concentrations will be > 3 UNL but if they were to be this elevated, the subject will be dropped from the study immediately.

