Record adjunctive therapeutic procedures (if performed i.e. Surgery) ⁶					X		
Standard of Care Radiology Results					X		
Clinical outcome				X		X	X
AEs and SAEs	X	X	X	X	X	X	
CBC with differential ⁷	X		X	X			
Chemistries (BUN, Creatinine, Alkaline Phosphatase, Bilirubin, AST, ALT) ⁷	X		X	X			
CRP and ESR ⁸	X	X	X	X	X	X	
Direct Coombs test	X			X			
Urine pregnancy test ⁹	X					X	
CrCl calculation	X				If Clinically Indicated		
Standard of Care Blood Culture ¹⁰			X				
Blood for PK analyses ¹¹			X				
Standard of Care Purulent Material From Bone ¹²			X				
Drug administration ¹³		X	X	X	X		

Abbreviations: AE = adverse event; CBC = complete blood count; CrCl = creatinine clearance; CRP = C-reactive protein; ESR = erythrocyte sedimentation rate; SAE = serious adverse event.

- 1 Perform baseline assessments within 24 hours before first dose of IV study drug.
- 2 Interval history focusing on the use of the involved extremity. On Month 12 follow up interval problems such as pathologic fractures and growth disturbances will be evaluated only.
- 3 The presence of warmth, tenderness, swelling, erythema, and movement of the infected extremity will be recorded specifically. The circumference of the infected extremity taken at the location of point tenderness will be determined.
- 4 Involved extremity will be assessed as at enrollment, if possible. Most of the subjects are expected to have surgical incision and drainage procedures and thus assessing the extremity for swelling, erythema, warmth and tenderness may not be possible because of drains in place and large surgical dressings that cannot be removed.
- 5 The degree of the subject's ability to ambulate will be assessed if the osteomyelitis is in the lower extremity-i.e. walks unaided, able to bear weight, can walk aid using a walker, etc. The use of upper and lower extremities will be assessed in terms of movement and range of motion.
- 6 Any surgical procedures will be documented and the findings described.
- 7 CBC and chemistries . If not done for SOC, collect samples for research if clinically indicated.
- 8 CRP and ESR will be collected typically as part of standard of care. If not performed for SOC, collect samples for research if clinically indicated.
- 9 Perform test if subject is a female who has reached menarche. If a pregnancy test is positive post baseline, follow reporting requirements in Section 11.1.4.

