 - Obtain blood sample for Alkaline Phosphatase, Bilirubin, AST and ALT, if clinically indicated.
 - If clinically indicated, estimate CrCl using the updated Schwartz "bedside" formula (Schwartz et al, 2009).
 - Collect results of blood cultures only if conducted per standard of care.

- Collect purulent material from bone only if a procedure is performed for standard of care when possible.
- PK Procedures:
 - Efforts will be made to obtain 1 PK blood sample (approximately 0.6 mL) at steady state from all subjects who received ceftaroline fosamil on Days 2 to 5 of treatment (only one PK sample collected on days 2-5) 4 hours (+/- 30 minutes) after the end of the infusion (before the start of the next infusion). PK samples may be collected after any infusion of ceftaroline fosamil on those days and before oral switch.
 - If purulent material is being obtained from bone or subperiosteal abscesses at surgery or via drainage by interventional radiology, we will attempt to obtain specimens for measurement of ceftaroline concentrations.

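### The 48-hour no-repeat rule for end-of-IV labs (Section 9.4) is not limited to post-dose samples, so a child stopped early may have no post-dose safety panel

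*Combined protocol and SAP*

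**What the plan says.** All references are to the combined protocol and SAP.

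- **Baseline.** Section 9.1 places baseline procedures in the 24 hours before the first dose. Section 1 makes an exception for the liver tests, "which will be obtained prior to administration of ceftaroline but the results may not be available", so a child may be dosed with AST/ALT pending.
- **Action on a high value.** If AST/ALT proves to be above 3 x ULN, Section 12.4 says "if they were to be this elevated, the patient subject will be dropped from the study immediately". Section 1 says the same. Section 7.7.1 lists this threshold among its off-study criteria, with others such as any urticarial rash.
- **EOIV after an early stop.** Section 9.4 times EOIV assessments within 24 hours of the last IV dose or "at time of premature discontinuation of study drug or early withdrawal from study (if on IV study drug)".
- **EOIV laboratory list.** Section 9.4 lists CRP, ESR, CBC with differential, BUN, creatinine, AST, ALT, alkaline phosphatase, bilirubin and Direct Coombs, all under this instruction: "If these assessments are performed within 48 hours of latest results, do not repeat these assessments".
- **Tests at completion.** Section 9.8.1 requires the liver tests and Direct Coombs before enrollment "and at the completion of ceftaroline treatment (EOIV visit)". Sections 1 and 12.4 require CBC, BUN, creatinine and the liver tests at baseline, weekly on ceftaroline and at its completion.
- **Analysis.** Section 12.1 bases safety on every child given at least one dose. Section 12.4 takes the last pre-dose assessment as baseline and summarises change from it.

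**The concern.** The no-repeat instruction has an obvious purpose: a child bled yesterday on treatment need not be bled again today. As worded, though, it does not ask whether the earlier sample was taken before or after the drug was started. When ceftaroline stops within the first day or two, the most recent result may be the baseline one. Followed to the letter, 9.4 then tells staff not to take the sample that Sections 1, 9.8.1 and 12.4 call for at completion.

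The primary objective is safety at the end of IV therapy. A dosed child with only a pre-dose panel has no laboratory change from baseline. For a child removed because of raised AST/ALT, the EOIV data would not show whether the value rose, fell or stayed level on drug. Direct Coombs is scheduled only at baseline and EOIV, so losing the EOIV test removes its only scheduled post-dose result.

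**Working it through.** **1. Does another scheduled test fill the gap?**

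- Days 2-14 (Section 9.3): "Obtain blood sample for Alkaline Phosphatase, Bilirubin, AST and ALT, if clinically indicated". CBC, BUN and creatinine carry the same condition, and Direct Coombs is not listed.
- The weekly test in Sections 1 and 12.4 is not yet due when the drug stops in the first two days.
- Weeks 2, 4 and 6 (9.5), EOT (9.6) and 12-month follow-up (9.7) list no AST/ALT, CBC or Direct Coombs. Creatinine clearance is estimated only if clinically indicated.

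No later visit schedules the panel.

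**2. When does the pre-dose result fall inside the 48 hours?**

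The rule does not say whether the 48 hours run from the draw or from the report, so both are checked. Let d = hours from draw to first dose (0 to 24, Section 9.1), t = hours from first dose to EOIV, and T = hours from draw to report. The documents give no value for T, so it is an assumption.

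- Counted from the draw, the baseline result qualifies if d + t ≤ 48. A sample drawn just before dosing (d = 0) covers EOIV up to t = 48 h; one drawn 24 h earlier covers up to t = 24 h.
- Counted from the report, it qualifies if d + t − T ≤ 48.
- For a usual course of at least 5 days, t is about 120 h. Counted from the draw, d + 120 always exceeds 48. Counted from the report, T would have to be at least 72 + d hours. The problem is therefore confined to early stops.

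**3. The child removed on a pending AST/ALT result**

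Assume exact q8h dosing (8 h intervals) and that drug stops when the result is known. For T > d:

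- doses given = ceil((T − d)/8)
- last dose at d + 8 × (doses − 1) hours after the draw, which is before T
- latest EOIV = last dose + 24 h, which is before T + 24

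| T (d = 0) | Doses | Last dose | Latest EOIV after draw |
|---|---|---|---|
| 6 h | 1 | 0 h | 24 h |
| 12 h | 2 | 8 h | 32 h |
| 24 h | 3 | 16 h | 40 h |
| 36 h | 5 | 32 h | 56 h |

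- T up to 24 h: latest EOIV is under 24 + 24 = 48 h after the draw for every d, after 1 to 3 doses. Every permitted EOIV time is inside the window.
- T between 24 and 48 h: EOIV done at removal is inside (1 to 6 doses); a later one may not be. With T = 36 h it falls between 36 and 56 h.
- T above 48 h: EOIV at or after removal is outside.
- Counted from the report, EOIV comes less than 24 h after it, so it is inside whatever T is.

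**4. Size**

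Section 7.9 replaces only children withdrawn before any study drug, so a dosed child stays among the 18. One such child is 1/18 = 5.6%, leaving 17/18 = 94.4% with a post-dose value.

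**The case against.** The best case against is that the plan, read as a whole, already requires the test. Section 9.8.1 asks for separate samples before enrollment and at EOIV, and Sections 1 and 12.4 also ask for a test at completion. Section 12.4 defines the last pre-dose value as baseline, so the same sample can hardly serve as the completion test too. That is probably what was intended. But none of those sections says the completion sample must be post-dose or that it overrides 9.4, and 9.4 is the instruction staff follow at the visit. The texts conflict for this child, and the conflict is easily removed.

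It is also fair that a repeat is likely in practice. An AST/ALT value that ends participation is a natural clinical indication. Section 10.5 requires adverse events to be followed to resolution or stability, which would ordinarily need a repeat if the elevation is recorded as an event. This stands: the gap is possible, not certain.

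A reader might infer more than the documents support:

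- **That such a child leaves with no safety assessment, because the plan says "the subject will be dropped from the study immediately".** Sections 7.7, 7.8.1 and 9.4 keep assessments after discontinuation, and 4.5 uses the same verb while retaining the safety assessment. Section 12.8 does not exclude an EOIV sample taken at removal.
- **That Table 1.1 footnote 7 makes the EOIV panel optional: "If not done for SOC, collect samples for research if clinically indicated".** The footnote also covers baseline chemistry, which other sections plainly require, so it cannot carry that weight.
- **That dosing with AST/ALT pending contradicts Sections 7.2 and 9.1.** It is a deliberate exception stated in Section 1, and starting treatment of an acute infection without waiting is reasonable.

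**Conclusion.** The point holds as a minor wording defect. Followed literally, Section 9.4 lets a pre-dose result stand in for the EOIV chemistry, CBC and Direct Coombs when ceftaroline stops within about 48 hours of the baseline sample or its report. That defeats the completion tests required elsewhere: the liver tests in Sections 1, 9.8.1 and 12.4, CBC, BUN and creatinine in Sections 1 and 12.4, and Direct Coombs in 9.8.1.

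The effect on the summary is small, at 5.6% of the 18 per child. The documents give no frequency for early stops and do not expect AST/ALT above 3 x ULN at baseline. With T up to 24 h, a child removed on a pending result has under 24 h of drug, short of the 48 h that Section 1 asks for to assess safety, so each such child adds little to the primary question. The dose counts and the window counted from the draw rest on the assumed turnaround. Counted from the report, the conclusion for this child does not depend on it.

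**What to change.** In Section 9.4, add one sentence: the 48-hour exemption applies only to results from samples drawn after the first dose of ceftaroline. Every dosed child is then due a post-dose safety panel at EOIV, and the same sentence covers chemistry, CBC and Direct Coombs. No other section needs to change, and clinical management is unaffected.

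The cost is one sentence of text and one extra blood draw in at most a few children, for tests the plan already requires at completion.
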